Table 11-1: Precision Estimate at Various Level of Predicted Protection Using Clopper Pearson CI (N=85)

Predicted Protection Level	Lower Bound of 95% CI	Upper Bound of 95% CI
95%	88%	99%
93%	85%	97%
91%	82%	96%

When the lower bound of 95% CI for the predicted protection after 2 doses of rF1V vaccine with CpG 1018 (ie, at Week 8) is similar to that (after 3 doses of rF1V vaccine (ie, at Week 30), the reduction of onset time to predicted rF1V protection is demonstrated.

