11.4 Immunogenicity Endpoints

The primary and other immunogenicity endpoints will be analyzed using the mITT population. Sensitivity analyses on immunogenicity data will also be presented using the PP population.

Immunogenicity will be measured by serum rF1V [REDACTED] concentration at each visit.

Part 2 Primary Objective 1: To assess the utility of a 2-dose schedule of rF1V vaccine with CpG 1018 as measured by reduction in time to onset of predicted rF1V protection

Endpoint: predicted protection (percentage of subjects reaching the [REDACTED] threshold that corresponds to 50% predicted vaccine efficacy) at Week 8 after 2 doses of rF1V vaccine with CpG 1018 as that at Week 30 after 3 doses of rF1V vaccine without CpG 1018

[figure not shown]
Percentage of subjects reaching the [REDACTED] threshold and associated 95% two-sided Clopper-Pearson confidence intervals will be computed. Fisher's exact tests will be used to compare predicted protection rate between study groups.

Criterion for evaluation: similar percentage of subjects reaching the [REDACTED] threshold that corresponds to 50% predicted vaccine efficacy after 2 doses of rF1V vaccine with CpG 1018 as compared to that after 3 doses of rF1V vaccine.

Part 2 Primary Objective 2: To assess the serum [REDACTED] concentration to rF1V vaccine with CpG 1018 compared with rF1V vaccine 28 days after the second dose of vaccine

Endpoint: Ratio of geometric mean ELISA concentration (GMC) between rF1V vaccine with CpG 1018 and rF1V vaccine at Week [REDACTED]

Criterion for evaluation: 2-times increase in [REDACTED] GMC point estimate after the second dose of rF1V vaccine with CpG 1018 to that after the second dose of rF1V vaccine.

Criteria for secondary objectives are GMC and seroconversion rate point estimates from rF1V vaccine with CpG 1018 to meet or exceed results from rF1V vaccine at relevant visits.

Data from Part 1 subjects and Part 2 subjects will be combined to evaluate the Part 2 objectives. No multiplicity adjustment is proposed as the Part 1 objectives are not evaluated against the 3-dose regime control group.

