3.0 STUDY OBJECTIVES AND ANALYSIS VARIABLES

Objectives	Endpoints
PART 1	
Primary	

 To select one of the two methods of administration of rF1V vaccine with CpG 1018 for Part 2 by comparing humoral immunization response 28 days after the second dose of vaccine 	
 Ratio of geometric mean ELISA concentration (GMC) between rF1V vaccine with CpG 1018 and rF1V vaccine
Secondary	

 To assess the safety and tolerability of rF1V vaccine with CpG 1018 compared with rF1V vaccine 	
 Rate of reactogenicity: solicited local and systemic post-injection reactions Rate of adverse events (AEs), severe AEs, serious adverse events (SAEs), immune-mediated adverse events of special interest (AESI), and deaths
PART 2	
Primary	

 To assess the utility of a 2-dose schedule of rF1V vaccine with CpG 1018 as measured by reduction in time to onset of predicted rF1V protection To assess the [REDACTED] antibody concentration to rF1V with CpG 1018 compared with rF1V vaccine 28 days after the second dose of vaccine 	
 Predicted protection (percentage of subjects reaching the [REDACTED] threshold that corresponds to 50% predicted vaccine efficacy) after 2 doses of rF1V vaccine with CpG 1018 compared to that of 3 doses of rF1V vaccine 
Criterion for evaluation: Similar percentage of subjects reaching the [REDACTED] threshold that corresponds to 50% predicted vaccine efficacy after 2 doses of rF1V vaccine with CpG 1018 at [REDACTED] compared to that after 3 doses of rF1V vaccine [REDACTED]
 
 Ratio of geometric mean ELISA concentration (GMC) between rF1V vaccine with CpG 1018 and rF1V vaccine 28 days after the second dose 
Criterion for evaluation: 2-times increase in [REDACTED] GMC point estimate after the second dose of rF1V vaccine with CpG

	
Criterion for evaluation: GMC and seroconversion rate point estimates from rF1V vaccine with CpG 1018 to meet or exceed results from rF1V vaccine at relevant visits

	

(Days 57 85 113 / Weeks 8 12 16) as

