4.0 SAMPLE SIZE CONSIDERATIONS

Part 2 primary objective 1 is to assess the utility of a 2-dose schedule of rF1V vaccine with CpG 1018 as measured by reduction in time to onset of predicted rF1V protection. The predicted protection will be based on a [REDACTED] meter threshold. Previous animal studies have established protective efficacy in animals. Since a human efficacy study is not feasible, an immunobridge from animal data to human data via the [REDACTED] test will be used to predict the protective efficacy in humans using a regression model. An initial predicted protection threshold will be calculated based on the data generated in this study in Group 3 after 3 doses of rF1V vaccine. Once the threshold is identified, it will be applied to the study groups to evaluate the Part 2 objectives. In addition to the previous animal studies conducted to establish protective efficacy, a new animal model utilizing rF1V vaccine with CpG 1018 will be developed to establish the protective level of antibody for CpG 1018 containing vaccines. Additional analyses will include a predicted protection threshold that will be calculated based on the data generated under the new animal model after 2 doses of rF1V vaccine with CpG 1018. In both instances, the animal-to-human immunobridge and the identification of the predicted protection thresholds will be documented in a separate report.

A similar approach was used to analyze the previous Phase 2a (NCT00332956) and Phase 2b (NCT01122784) study data using the animal model from the previous animal studies. Thresholds that corresponded to 50% predicted protective efficacy in humans were established for those trials. In a pooled analysis of these previous immunobridge studies, 93% (95% Clopper Pearson confidence interval [CI] = 85%, 98%) of subjects reached the predicted protection threshold.

It is assumed that a similar percentage of the subjects in Group 3 will reach the threshold identified in this study. When this threshold is applied to both Part 2 study groups, a similar lower bound of the 95% CI is desired across the groups. Table 4-1 shows the lower bound of 95% Clopper Pearson CI for different observed levels of predicted protection assuming 85 of the 90 planned subjects (Part 1 N = 20 and Part 2 N =70) will have data available for the evaluation. Thus, with a predicted protection level of 93%, the lower bound of the 95% CI would be 85%.

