Table 4-1: Precision Estimate at Various Level of Predicted Protection Using Clopper Pearson CI (N=85)

Predicted Protection Level	Lower Bound of 95% CI	Upper Bound of 95% CI
95%	88%	99%
93%	85%	97%
91%	82%	96%

When the lower bound of 95% CI for the predicted protection after 2 doses of rF1V vaccine with CpG 1018 (ie, at Week 8) is similar to that after 3 doses of rF1V vaccine (ie, at Week 30), the reduction of onset time to predicted rF1V protection is demonstrated.

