8.0 STATISTICAL METHODS

This is a phase 2, randomized, active-controlled, observer-blinded, multicenter trial of the immunogenicity, safety, and tolerability of rF1V vaccine with CpG 1018 compared with rF1V vaccine alone in adults.

Part 1 objectives will be evaluated descriptively. The administration method of vaccine utilized in Part 2 of the study will be selected by Dynavax in consultation with the Department of Defense (DoD) after Day 57 immunogenicity data become available to determine whether the GMC 1 month after 2 doses of rF1V vaccine with CpG 1018 using the selected administration method is at least 2 times higher than that 4 weeks after 2 doses of rF1V vaccine in Group 3.

The proposed statistical planning for Part 2 is presented according to the objectives. Data from Part 1 and Part 2 will be combined to evaluate the Part 2 objectives. No multiplicity adjustments are made, and all statistical tests will be conducted at 5% two-sided Type I level unless otherwise specified. All confidence intervals are two-sided 95% confidence intervals unless otherwise specified.

All analyses of demographics and baseline characteristics, medical history, vaccine exposure and safety will be summarized in a descriptive manner. In general, continuous variables will

be summarized by number of subjects, mean, standard deviation, median, quartiles, minimum and maximum, and categorical variables will be summarized by number and percentage of subjects in each study group as appropriate. All data processing, summarization, and analyses will be performed using SAS Version 9.4 or higher. Specifications for tables, graphs, and data listings will be provided in the tables, figures, listings (TFL) specifications document as needed. No specific safety hypotheses will be tested.

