Estimand: Percentage of subjects reaching the [REDACTED] threshold and associated 95% two-sided Clopper-Pearson confidence intervals will be computed. Fisher's exact tests will be used to compare predicted protection rate between study groups.

Criterion for evaluation: Similar percentage of subjects reaching the [REDACTED] threshold that corresponds to 50% predicted vaccine efficacy after 2 doses of rF1V vaccine with CpG 1018 as compared to that after 3 doses of rF1V vaccine.

Part 2 Primary Objective 2: To assess the serum [REDACTED] concentration to rF1V vaccine with CpG 1018 compared with rF1V vaccine 28 days after the second dose of vaccine

Endpoint: Ratio of geometric mean ELISA concentration (GMC) between rF1V vaccine with CpG 1018 and rF1V vaccine at Week [REDACTED].

Estimand: GMCs and associated two-sided 95% confidence intervals will be computed by exponentiating the mean and associated Student's t confidence interval of the log10 transformed individual antibody concentrations assuming Normal distribution. The ratio of GMCs and associated two-sided 95% confidence interval will be compared between rF1V vaccine with CpG 1018 and rF1V vaccine, using ANOVA if site can be used as an adjustment factor in the model or Student's t method.

Criterion for evaluation: 2-times increase in [REDACTED] GMC point estimate after the second dose of rF1V vaccine with CpG 1018 to that after the second dose of rF1V vaccine.

Part 2 Secondary Objective: To assess the serum [REDACTED] concentration to rF1V with CpG 1018 at selected time points after each dose

Endpoint: GMC and seroconversion rate of serum rF1V [REDACTED] titers at the following selected time points after each dose of vaccine:

- [REDACTED]

- [REDACTED]

[figure not shown]
Seroconversion is defined as the presence of detectable antibody in subjects who had no detectable antibody levels at Day 1, or a 2: 2-fold increase in antibody level in subjects who had detectable antibody levels at Day 1.

Estimand: GMCs and associated two-sided 95% confidence intervals will be computed by exponentiating the mean and associated Student's t confidence interval of the log10 transformed individual antibody concentrations assuming Normal distribution.

Seroconversion rate and associated 95% two-sided Clopper-Pearson confidence intervals will be computed.

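### Matching CpG at Week 8 to rF1V alone at Week 30 does not by itself show earlier onset; the concurrent Week 8 difference in predicted protection should be estimated and reported with any onset statement

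*SAP*

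**What the plan says.** Part 2 Primary Objective 1 is to assess the two-dose schedule "as measured by reduction in time to onset of predicted rF1V protection" (SAP 4.0). Protocol 11.4 sets the endpoint as predicted protection "at Week 8 after 2 doses of rF1V vaccine with CpG 1018 as that at Week 30 after 3 doses of rF1V vaccine". The decision sentence follows the precision table in both documents. When the lower 95% bounds at those two visits are similar, SAP 4.0 ends "ie, at Week 30), the reduction of onset time to predicted rF1V protection is demonstrated", and Protocol 11.1 has the same conclusion: "the reduction of onset time to predicted rF1V protection is demonstrated".

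For the analysis, SAP 8.6 gives Clopper-Pearson intervals and adds "Fisher's exact tests will be used to compare predicted protection rate between study groups", without naming a visit.

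The concurrent comparisons that can be read use other measures. Part 2 Primary Objective 2 looks for a two-fold rise in the "GMC point estimate after the second dose of rF1V vaccine with CpG 1018 to that after the second dose of rF1V vaccine" (SAP 8.6). The secondary objective compares GMC and seroconversion at selected visits. No readable sentence makes the onset conclusion depend on any of these.

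Part of the objectives table in SAP 3.0 is redacted. A surviving fragment reads "Days 57 85 113 / Weeks 8 12 16) as", so some analysis at Weeks 8, 12 and 16 exists that cannot be read.

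**The concern.** A reduction in onset time is relative to something, and here the comparator is rF1V alone. To say that CpG brought predicted protection forward, one needs to know how many Group 3 subjects were already above the threshold at Week 8. The decision sentence uses Group 3 only at Week 30. It therefore gives the same answer whether Group 3 was far below the threshold at Week 8 or already at its Week 30 level.

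A reader of the conclusion will take it as a gain over rF1V alone at the earlier time. The size of that gain is not part of what was shown. If rF1V alone is already high at Week 8, the gain could be small while the conclusion is worded as strongly as ever.

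The point concerns the wording of the conclusion and the reporting. Comparing completed regimens at their own time points is reasonable and should stay. How similarity is defined is a separate matter.

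**Working it through.** **Inputs.** 85 evaluable of 90 planned per group, and about 93% expected in Group 3 after three doses (SAP 4.0). The readable text gives no Group 3 rate at Week 8, so a range is assumed.

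**1. The plan's own table.** Exact Clopper-Pearson limits at n = 85, using the beta quantiles B(0.025; x, n−x+1) and B(0.975; x+1, n−x):

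- 81/85: 88.4% to 98.7%
- 79/85: 85.3% to 97.4%
- 77/85: 82.3% to 95.8%

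These reproduce SAP Table 4-1 (88–99, 85–97 and 82–96).

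**2. The rule.** Take CpG 79/85 at Week 8 and Group 3 79/85 at Week 30. Both lower bounds are 85.3%, so the rule is met exactly. Group 3 at Week 8 does not enter.

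**3. The concurrent Week 8 difference.** With d = p1 − p2 (CpG minus Group 3) and Wilson limits (l, u) for each rate, the Newcombe limits are d − √[(p1−l1)² + (u2−p2)²] and d + √[(u1−p1)² + (p2−l2)²].

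Worked case, 79/85 against 68/85: p1 = 0.9294 (Wilson 0.8544 to 0.9672), p2 = 0.8000 (0.7028 to 0.8712).

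- d = 0.1294
- Lower: 0.1294 − √(0.0750² + 0.0712²) = 0.026
- Upper: 0.1294 + √(0.0378² + 0.0972²) = 0.234

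| Group 3 at Week 8 (assumed) | Difference, points | 95% CI |
|---|---|---|
| 23/85 (27.1%) | +65.9 | 53.2 to 75.0 |
| 60/85 (70.6%) | +22.4 | 10.9 to 33.4 |
| 64/85 (75.3%) | +17.6 | 6.7 to 28.5 |
| 68/85 (80.0%) | +12.9 | 2.6 to 23.4 |
| 72/85 (84.7%) | +8.2 | −1.5 to 18.1 |
| 76/85 (89.4%) | +3.5 | −5.4 to 12.7 |
| 79/85 (92.9%) | 0.0 | −8.4 to 8.4 |

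The rule is met identically in every row. The first row is close to the 26.7% Week 8 rate of the alum-adjuvanted comparator in the hepatitis B trial in adults 18 to 55 (Protocol 2.4.2.1.1), which used a different antigen. In that row the gap has no consequence.

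**4. How likely is a plainly false claim?** Suppose CpG adds nothing. The chance of a GMC ratio of 2 or more is the normal tail beyond log10(2) / (SD × √(2/85)), where log10(2) = 0.301:

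- Assumed log10 SD 0.5: 0.301/0.0767 = 3.92, P = 0.00004
- Assumed log10 SD 0.8: 0.301/0.1227 = 2.45, P = 0.007

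The joint event (GMC ratio of at least 2, and CpG at Week 8 similar to Group 3 at Week 30) was simulated with 200,000 log-normal trials per setting. Settings were Group 3 at 93% at Week 30, Week 8 rates of 80 to 90%, and an assumed correlation of 0.7 between Group 3's two visits. Similarity was read as a non-significant Fisher test, or as rates within 5 or 10 points. The joint probability is at most about 0.7%.

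**5. Why estimation rather than a test.** Exact two-sided Fisher power at Week 8 (5%, CpG higher), with CpG at 93%, is 65%, 31% and 6.5% when rF1V alone is at 80%, 85% and 90%. For a true 3-fold gain from 90%, the CpG rate is Φ(z(0.90) + log10(3)/SD). That is 98.7% or 97.0% at SD 0.5 or 0.8, with power 61% or 34%. A significance gate would often reject a reduction that is real but modest. The interval still informs there: 84/85 against 77/85 gives +8.2 (1.3 to 16.4), and 82/85 against 77/85 gives +5.9 (−1.9 to 14.3).

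**The case against.** The strongest reply is that Week 8 is already compared concurrently at primary level. Primary Objective 2 gives a GMC ratio with a confidence interval and a 2-fold criterion 28 days after dose 2, and the secondary endpoints add GMC and seroconversion. Before Part 2, the sponsor also asks whether the chosen method at least doubles Group 3's GMC at Day 57. In a simulation with 20 per group and the better of two methods chosen, an adjuvant with no effect passes that check in about 5% (log10 SD 0.5) to 19% (SD 0.8) of trials. So the worst case is screened twice.

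The decision sentence also stands only in the sample-size sections; the analysis sections ask only for a similar percentage. Key visits and an exploratory objective are redacted, so a Week 8 comparison may already be planned. Finally, the proposed wording sets no decision rule.

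Much of this stands. It makes the practical risk low, and it rules out any claim that no Week 8 analysis is planned. It does not rescue the sentence, because no readable text ties the onset conclusion to any of these results. Nor does a GMC ratio size the gain in predicted protection: under a log-normal model, a true 2-fold shift adds about 15 to 23 points if Group 3 is at 50%, but only about 5 to 7 if it is at 90% (log10 SD 0.8 to 0.5). The absence of a decision rule is deliberate, since a test there would be underpowered.

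**Conclusion.** The concern holds and should be fixed. The onset conclusion in SAP 4.0 and Protocol 11.1 goes beyond the contrast it rests on: the rule is met identically for Week 8 differences from +65.9 points to 0.

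The practical risk is limited. If rF1V alone is far below the threshold at Week 8, nothing changes. The gap matters mainly if it is already at about 80% or more, where the difference shrinks to about 13 points or less with CpG at 93%. A claim that is false because CpG does nothing would also have to pass the 2-fold GMC criterion, which is very unlikely.

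This rests on 85 evaluable per group, the 93% planning rate, assumed Week 8 rates and assumed log10 SDs of 0.5 to 0.8. Confidence is moderate because redacted text may already contain the comparison. A Week 8 difference shows earlier protection at that visit; it does not measure weeks saved.

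**What to change.** 1. **SAP 8.6, Part 2 Primary Objective 1.** Add: *Predicted protection at Week 8 will also be estimated in the CpG group and Group 3, using the same threshold, in mITT subjects with a Week 8 result. Each rate will be given with its 95% Clopper-Pearson CI, and the difference (CpG minus Group 3) with its 95% Newcombe CI. This is estimation; no test of this difference decides the objective.*
2. **By-visit table.** Show the proportion at or above the threshold by group at every scheduled visit.
3. **SAP 4.0 and Protocol 11.1.** Reword the decision sentence: *If the lower bounds for CpG at Week 8 and Group 3 at Week 30 are similar, the two-dose CpG regimen at Week 8 is considered similar to the three-dose regimen at Week 30. Any statement of reduced time to onset will be reported with, and interpreted by, the estimated Week 8 difference and its 95% CI.*

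If redacted text already holds the comparison, refer to it from SAP 4.0 instead of adding item 1.

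**Cost.** One estimate, one table and one sentence in each document, with no new samples or visits and no alpha spent. The method choice is already made "after Day 57 immunogenicity data become available" by comparing CpG with Group 3, concentration is measured at each visit (SAP 8.6), and SAP 6.2 sets the denominator for by-visit percentages. The downside is a less emphatic conclusion if rF1V alone is already high at Week 8. The interval will then often include zero, which must not be read as no benefit of CpG.

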5.0 ANALYSIS POPULATIONS

5.1 Enrolled Population

The enrolled population is defined as all subjects who enrolled in the study.

5.2 Safety Population

The Safety Population will comprise all subjects who receive at least 1 dose of the study vaccine, excluding subjects who have no on-study data.

5.3 Immunogenicity Population

The modified intent-to-treat (mITT) population will comprise all eligible subjects who received at least 1 dose of study vaccine and have a post-injection immunogenicity evaluation.

The per-protocol (PP) population for the immunogenicity analyses will comprise Groups 1 and 2 subjects who received 2 doses of study vaccine and Group 3 subjects who received 3 doses of study vaccine, have no major protocol deviations (see Section 8.2), and have immunogenicity data obtained within the study visit window at Day █ for Groups 1 and 2 and Day █ for Group 3.

Note: the PP population definition and major protocol deviations in Section 8.2 are updated from the Protocol Amendment 5.

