7.5 Concomitant Medications

7.5.1 Prohibited Treatments or Therapies

The following non-study medications are prohibited:

- **Any licensed COVID-19 vaccine or inactivated vaccine (including vaccines containing mRNA or CpG)**
 - :S 14 days prior to each study injection through 14 days after each study injection
- **Any live vaccine**
 - :S 28 days prior to each study injection through 28 days after each study injection

- **Other concomitant medications**

- :S 28 days prior to vaccine injection (Day 1) through 28 days after the third study vaccine injection Week 26 (Day 183):
 - Systemic corticosteroids (more than 3 consecutive days) or other immunomodulators or immunomodulators immune suppressive medication, with the exception of inhaled steroids
 - Any other investigational medicinal agent
- :S 90 days prior to vaccine injection (Day 1) and through 28 days after the third study vaccine injection Week 26 (Day 183):
 - Granulocyte or granulocyte-macrophage colony-stimulating factor
 - Immunoglobulins or any blood products
 - Antisense oligonucleotides
 - Drugs/investigational agents with very long half-lives (defined as 2' 60 days)
- At any time prior to vaccine injection (Day 1) and through 28 days after the third study vaccine injection Week 26 (Day 183):
 - DNA plasmids or other genetic therapy intended to integrate permanently into host cells

If a subject requires treatment that is prohibited, **the subject will not be withdrawn from the study** but will be followed for safety through Week 56.

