8.2 Protocol Deviations

For the purpose of selecting subjects for the per-protocol population, a major protocol deviation is defined as one of the following:

- not meeting one or more enrollment criteria,
- vaccine was not given per-protocol,
- [REDACTED] serum sample obtained outside protocol specified visit window 4 weeks following the second study injection for rF1V vaccine with CpG 1018 groups ([REDACTED]) and the third study injection for rF1V vaccine only group ([REDACTED]).

This deviation will be identified at both visits, but will be applied for each group by corresponding visit for exclusion purpose post database lock (DBL), as this deviation is dependent upon treatment assignment for complete adjudication, e.g. a subject who was vaccinated per protocol but who had the Day [REDACTED] blood sample drawn out of window, is marked as a major protocol deviation. Following DBL and unblinding, if the subject is found to be in the rF1V vaccine with CpG-1018 group, although the out of window of the sample is considered a major protocol deviation, the subject will be included in the per protocol analysis set provided no other major protocol deviations apply.

- received prohibited concomitant medications.

The following non-study medications are prohibited for the purpose of evaluating per-protocol population:

- Any licensed COVID-19 vaccine or inactivated vaccine (including vaccines containing mRNA or CpG)
 - :S 14 days prior to each study injection through 14 days after each study injection
- Any live vaccine
 - :S 28 days prior to each study injection through 28 days after each study injection
- Other concomitant medications

- :S 28 days prior to vaccine injection (Day 1) through 28 days after the third study vaccine injection [REDACTED]
 - Systemic corticosteroids (more than 3 consecutive days) or other immunomodulators or immunomodulators immune suppressive medication, with the exception of inhaled steroids
 - Any other investigational medicinal agent
- :S 90 days prior to vaccine injection (Day 1) and through 28 days after the third study vaccine injection [REDACTED]
 - Granulocyte or granulocyte-macrophage colony-stimulating factor
 - Immunoglobulins or any blood products
 - Antisense oligonucleotides
 - Drugs/ investigational agents with very long half-lives (defined as 2: 60 days)
- At any time prior to vaccine injection (Day 1) and through 28 days after the third study vaccine injection [REDACTED]

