8.6 Immunogenicity Analyses

The primary and other immunogenicity endpoints will be analyzed using the mITT population. Sensitivity analyses on immunogenicity data will also be presented using the PP population.

Immunogenicity will be measured by serum rF1V [REDACTED] concentration at each visit.

Data from Part 1 subjects and Part 2 subjects will be combined to evaluate the Part 2 objectives. No multiplicity adjustment is proposed.

Additional analyses may be attempted, including analysis to quantify antibody decay over time.

Part 1 Primary Objective: To select one of the two methods of administration of rF1V vaccine with CpG 1018 for Part 2 by comparing humoral immunization response 28 days after the second dose of vaccine

Endpoint: Ratio of geometric mean ELISA concentrations (GMCs) between rF1V vaccine with CpG 1018 and rF1V vaccine.

Estimand: GMCs and associated two-sided 95% confidence intervals for each of the 3 study groups will be computed by exponentiating the mean and associated Student's t confidence interval of the log10 transformed individual antibody concentrations assuming Normal distribution. The ratio of GMCs and associated two-sided 95% confidence interval will be compared between rF1V vaccine with CpG 1018 and rF1V vaccine, using Student's t method. The ratio of GMCs and associated two-sided 95% confidence interval between two administration methods of rF1V vaccine with CpG 1018 vaccines will also be produced.

Criterion for evaluation: GMC 1 month after 2 doses of rF1V vaccine with CpG 1018 using the selected administration method is at least 2 times higher than that 4 weeks after 2 doses of rF1V vaccine.

Part 2 Primary Objective 1: To assess the utility of a 2-dose schedule of rF1V vaccine with CpG 1018 as measured by reduction in time to onset of predicted rF1V protection

Endpoint: Predicted protection (percentage of subjects reaching the [REDACTED] threshold that corresponds to 50% predicted vaccine efficacy) at Week [REDACTED] after 2 doses of rF1V vaccine with CpG 1018 as that at Week [REDACTED] after 3 doses of rF1V vaccine without CpG 1018. The [REDACTED] threshold that corresponds to 50% predicted vaccine efficacy will be obtained from a model using [REDACTED] data after 3 doses of rF1V vaccine (or after 2 doses of rF1V

with CpG 1018 TBD) in this study. The threshold and the model used will be described in a separate report. Part 2 Primary Objective 1 can only be evaluated after the determination of this threshold.

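### The single per-protocol set fits Primary Objective 1 but applies arm-specific and post-endpoint exclusions to the Week 8 GMC ratio of Primary Objective 2

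*SAP*

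**What the plan says.** SAP 5.3 defines one PP set. It consists of "Groups 1 and 2 subjects who received 2 doses of study vaccine and Group 3 subjects who received 3 doses of study vaccine", without major deviations and with "immunogenicity data obtained within the study visit window at Day" (day numbers blacked out, a different day for each arm).

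SAP 8.2 identifies those visits in words. A major deviation is a "serum sample obtained outside protocol specified visit window 4 weeks following the second study injection for rF1V vaccine with CpG 1018 groups", and for the rF1V-only group the same rule is tied to the third injection. The rule is arm-specific at the exclusion step: "This deviation will be identified at both visits, but will be applied for each group by corresponding visit for exclusion purpose". The SAP's own example keeps a CpG subject in the set despite an out-of-window sample at a visit that does not count for that arm.

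SAP 8.2 also excludes for prohibited medication. For steroids, immunomodulators and other investigational agents the period runs from "28 days prior to vaccine injection (Day 1) through 28 days after the third study vaccine injection". The later end is the same for the other listed drug classes apart from vaccines, and it does not differ by arm.

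SAP 8.6 analyses the immunogenicity endpoints in the mITT population and adds: "Sensitivity analyses on immunogenicity data will also be presented using the PP population". It makes no exception for Part 2 Primary Objective 2, which compares both arms 28 days after dose 2 and is judged by a GMC-ratio point estimate of 2.

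**The concern.** A PP analysis should show whether the mITT result survives when subjects whose endpoint may have been distorted by protocol deviations are removed. For the Week 8 GMC ratio, the set does something else.

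- **Later events, Group 3 only.** A Group 3 subject with two correct doses and a valid Week 8 sample leaves the set if dose 3 or the in-window Week 30 sample is missed. Nothing at those visits can change the Week 8 titre.
- **Week 8 window, CpG only.** An out-of-window Week 8 sample removes a CpG subject and keeps a Group 3 subject, although that sample is the endpoint for both.
- **Later medication, both arms.** A prohibited drug taken months after the Week 8 sample removes the subject.

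The first route need not be random. Protocol 5.3 ends further injections after certain reactions. A CpG subject stopped after dose 2 has already met the two-dose requirement; a Group 3 subject stopped for the same reason cannot meet the three-dose one.

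At stake is interpretation. If mITT and PP differ on Objective 2, the reader cannot tell a deviation effect from selection after the endpoint.

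**Working it through.** **Inputs.** Week 8 and Week 30 endpoints: Protocol 11.4 and SAP 4.0. Third injection at Week 26 (Day 183): Protocol 7.5.1. Expected data: 85 of 90 per group, SAP 4.0. Criterion of 2: SAP 8.6. The documents give no PP exclusion rate, no titre difference between excluded and retained subjects, and no SD.

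**The plan's own figure.** The only design calculation is the Clopper-Pearson table. It reproduces: 79/85 gives 85.3% to 97.4% (stated 85%, 97%). It concerns Objective 1 and does not bear on the PP set.

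**Timing.** Dose 3 comes 26 - 8 = 18 weeks after the Week 8 sample, and the Week 30 sample 30 - 8 = 22 weeks after it. The medication period ends at Day 183 + 28 = Day 211, which is 211 - 57 = 154 days (22 weeks) after Day 57.

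**Rules side by side for the Week 8 ratio**

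| Event | CpG subject | Group 3 subject |
|---|---|---|
| Week 8 sample out of window | excluded | kept |
| Week 30 sample missing or out of window | kept | excluded |
| Only two active doses received | kept | excluded |
| Prohibited drug between Week 8 and Day 211 | excluded | excluded |

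The SAP does not say whether a missed third-visit placebo in a CpG subject counts as vaccine not given per protocol.

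**Size, route 1 (later events in Group 3).** Let f be the share of Group 3 removed and d the log10 amount by which their Week 8 titres lie below those of the retained subjects. The full-group log mean is f x d below the retained mean, so

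PP ratio = 2.0 x 10^(-f x d), or 2.0 x 10^(+f x d) if the removed subjects are the higher responders.

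Both f and d are assumptions. The value f = 5/90 borrows the plan's missing-data allowance.

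| f | d = 0.1, removed lower / higher | d = 0.3, removed lower / higher |
|---|---|---|
| 5% | 1.977 / 2.023 | 1.932 / 2.070 |
| 5/90 = 5.6% | 1.975 / 2.026 | 1.925 / 2.078 |
| 10% | 1.954 / 2.047 | 1.867 / 2.143 |
| 15% | 1.932 / 2.070 | 1.803 / 2.218 |

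With a wider assumed difference of 1.5- to 3-fold, f = 5/90 gives a factor of 1.5^(5/90) = 1.023 to 3^(5/90) = 1.063, a shift of about 2-6%.

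**Size, route 2 (out-of-window Week 8 samples kept in Group 3 only).** Let a share w of Group 3 have such samples, with GMC differing by a factor g from the in-window samples. A ratio of 2.0 among in-window samples becomes 2.0 x g^(+w) or 2.0 x g^(-w). For w = 5%, g = 1.25: 2.022 or 1.978. For w = 15%, g = 2: 2.219 or 1.803.

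**Route 3 (later medication).** The log10 ratio shifts by (f x d in the CpG arm) - (f x d in Group 3). If the two products are equal, the shift is zero. This route loses valid Week 8 data from the PP table but has no built-in arm asymmetry.

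**The case against.** The strongest reply is that no decision rests on this set. The primary analysis is mITT, PP is an added presentation, and no passage requires PP to reach the 2-fold criterion. That stands. A reader might infer that the flaw could make the trial fail Objective 2, or that valid Week 8 data are lost to the trial; mITT keeps a Group 3 subject who later misses dose 3, so the documents support neither.

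The arm-specific rule is also deliberate. It matches Objective 1, SAP 5.3 declares the change from the protocol, and the revision history records it. So it should not be read as a contradiction or as a general defect of the PP definition. The difficulty arises only where the same set is carried to comparisons at a common visit.

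The medication period is the same for all groups, so it cannot be called an arm-specific exclusion. Nor is PP the only further analysis for both primary objectives: for Objective 1, SAP 4.0 plans a second threshold from a new animal model. For Objective 2, PP is the only sensitivity analysis named.

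Finally, the shift is modest. With an assumed SD of 0.3-0.6 log10 and 85 per arm, the standard error of the log10 ratio is SD x sqrt(2/85) = 0.046-0.092; the largest tabulated route 1 shift is 0.15 x 0.3 = 0.045, below one standard error. That stands as a statement of size. It does not remove the point: mITT and PP share most of their subjects, so much sampling error is common to both, and the comparison between them is what the sensitivity analysis is for.

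**Conclusion.** The point holds for the PP analysis of Primary Objective 2 and for other comparisons of the arms at the same visit. The dose and sample-window rules select the two arms differently at Week 8, and in Group 3 they select on events 18 to 22 weeks after the endpoint. The later medication rule is over-restrictive in both arms. The mITT analysis is unaffected, and the dose and window rules remain suitable for Objective 1.

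Neither size nor direction can be derived from the documents. Under the assumptions shown for route 1, a true ratio of 2.0 would read 1.80-1.98 or 2.02-2.22 for 5-15% removed, and 1.925-1.975 or 2.026-2.078 at the planned 5/90 loss. Because the criterion is a bare point estimate, a small shift matters only when the ratio is close to 2. A reader might conclude that the rule favours one arm; nothing in the documents supports a direction. The change is still worth making, because it costs little and makes the sensitivity analysis interpretable.

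**What to change.** In SAP 5.3 and 8.2:

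1. Keep the current dose and sample-window rules of the PP set for Primary Objective 1.
2. For Primary Objective 2 and every other same-visit comparison, define a visit-specific PP set with identical rules in both arms: enrolment criteria met; all injections scheduled before that visit given per protocol; that visit's sample in window; and no prohibited medication up to that sample.
3. Say in 8.6 which PP set each table uses.

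Defining the set visit by visit means that no visit is conditioned on later events, and it supplies a rule for visits before Week 8, between Weeks 8 and 30, and after Week 30. Under the Week 8 set, the selection routes shown above no longer differ by arm by rule.

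Cost: SAP wording, visit-level PP flags, and PP denominators that vary by visit. No new data are needed.
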